12.4 Replacement of Subjects

Subjects who withdraw from the study treatment will not be replaced.

Subjects who withdraw from the study will not be replaced.

13 PROTOCOL VIOLATIONS

A protocol violation occurs when the subject or investigator fails to adhere to significant protocol requirements affecting the inclusion, exclusion, subject safety and primary endpoint criteria. Protocol violations for this study include, but are not limited to, the following:

Failure to meet inclusion/exclusion criteria

Failure to apply ingenol mebutate 0.015% gel per protocol.

Use of a prohibited concomitant medication

Failure to comply with Good Clinical Practice (GCP) guidelines will also result in a protocol violation.

When a protocol violation occurs, it will be discussed with the investigator and a Protocol Violation Form detailing the violation will be generated. This form will be signed by the Investigator. A copy of the form will be filed in the site's regulatory binder.

14 DATA SAFETY MONITORING

Due to the scope of this study, there will be no formal Data Safety Monitoring Board (DSMB) or Data Monitoring Committee (DMC). This is an open-label, single-center study for an FDA-approved medication, and the investigator will have access to all study data.

15 STATISTICAL METHODS AND CONSIDERATIONS

Prior to the analysis of the final study data, a detailed Statistical Analysis Plan (SAP) will be written describing all analyses that will be performed. The SAP will contain any modifications to the analysis plan described below.

15.1 Data Sets Analyzed

All eligible patients who are enrolled in the study and receive at least one dose of the study drug (the Safety Population) and who have had at least one post-baseline safety evaluation will be included in the safety analysis.

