CONCOMMITANT MEDICATIONS	
Allowed: Bland topical emollients such as Eucerin, Cetaphil. 1% topical hydrocortisone cream or ointment allowed after D4 at the discretion of the investigator.
 
Prohibited: Any topical prescription medication on the treatment area during the study.

EVALUATIONS	
PRIMARY ENDPOINT	
The primary outcome will be the safety endpoint of the incidence rate of patients who experience:
 
 1) Any adverse event (AE) ascertained by patient report, physician evaluation, or laboratory value. 2) One or more serious adverse events (SAE) as defined by CTCAEv4 3) Adverse events leading to study drug discontinuation.
SECONDARY ENDPOINTS	
Efficacy:
 
 • Reduction in number of actinic keratoses: defined as the percent change in actinic keratosis count in the target treatment area on Day 57, as compared to the baseline lesion count. • Partial clearance of lesions: defined as the proportion of patients with a reduction of 75% or more in the number of clinically visible AKs in the target treatment area at Day 57, compared to baseline. • Complete clearance of lesions: defined as the proportion of patients with complete clearance of actinic keratoses in the target treatment area. 
Local skin response:
 
 • Local skin response (LSR) as measured by visual assessment by the investigator using a 4 point scale on six responses for a maximum total of 24, according to the LSR scoring scale. 
Patient Reported Outcomes:
 
 • Pain as measured by the 0-10 VAS Numeric Pain Distress Scale (0 = no pain, 5 = moderate pain, 10 = unbearable pain). • Patient quality of life as measured by Skindex-16 survey
STATISTICS Primary Analysis Plan	
This is a small descriptive study, with the primary safety endpoint of the incidence rate of patients who experience:
 
 1) Any adverse event (AE) ascertained by patient report, physician evaluation, or laboratory value, 2) One or more serious adverse events (SAE) as defined by CTCAEv4, and 3) Adverse events leading to study drug discontinuation. 
The safety analysis will be based on the safety population, which is defined as all randomized patients who have received at least one dose of study medication and who have had at least one post-baseline

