4 STUDY DESIGN

4.1 Study Overview

This is a single arm, open-label interventional study of ingenol mebutate 0.015% in solid organ transplant recipients. Twenty subjects are planned; 10 kidney transplant recipients and 10 lung transplant recipients. These populations have been selected as they represent the spectrum of solid organ transplantation: kidney transplant recipients are the largest transplant population, but have lower levels of immunosuppression and skin cancer risk. Lung transplant recipients have the highest burden of skin cancer and actinic keratoses.

Screening data will be reviewed to determine subject eligibility. Subjects who meet all inclusion criteria and none of the exclusion criteria will be enrolled into the study.

The following treatment regimens will be used:

- Experimental treatment: Ingenol mebutate 0.015%, topical gel
- Placebo or Comparator: None

Total duration of subject participation will be 57 days. Total duration of the study is expected to be 8 months.

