8 STUDY TREATMENTS

8.1 Method of Assigning Subjects to Treatment Groups

All eligible subjects that have enrolled in the study will be supplied with open-label ingenol mebutate 0.015% gel. The investigator or study staff will record the kit number dispensed to each subject.

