9.1.10 Adverse Events

Information regarding occurrence of adverse events will be captured throughout the study. Duration (start and stop dates and times), severity/grade, outcome, treatment and relation to study drug will be recorded on the case report form (CRF).

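### Section 15.1 makes eligibility a condition of the primary safety analysis and the synopsis does not; read literally, a dosed subject later judged ineligible could leave the primary rate

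*Combined protocol and SAP*

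**What the plan says.** The primary endpoint (synopsis; Sections 5.1 and 15.3) is the incidence of patients with any adverse event, with a serious adverse event, and with an adverse event leading to discontinuation of study drug. Its denominator is described twice.

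- Section 15.1 takes "All eligible patients who are enrolled in the study and receive at least one dose of the study drug (the Safety Population") and adds that those "who have had at least one post-baseline safety evaluation will be included in the safety analysis".
- The synopsis, under Statistics, defines the safety population as "all randomized patients who have received at least one dose of study medication and who have had at least one post-baseline" safety evaluation.

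Both require a dose and a post-baseline safety evaluation. They differ in the opening condition: eligible and enrolled in one, randomized in the other.

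Three other places bear on the word *eligible*. Section 4.1 states the entry rule: "Subjects who meet all inclusion criteria and none of the exclusion criteria will be enrolled into the study". Section 8.1 uses a phrase close to that of 15.1: "All eligible subjects that have enrolled in the study will be supplied with open-label ingenol mebutate 0.015% gel". Section 13 lists, among protocol violations, "Failure to meet inclusion/exclusion criteria".

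**The concern.** A safety set should depend on exposure. If eligibility is also a condition, a subject who received the drug and is later found not to have met a criterion can be left out of the analysis together with his or her events.

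Two features of this protocol make the question more than verbal. First, the entry criteria are not one fixed set. Section 6.2 (item 5) restricts the qualifying lesions to non-hyperkeratotic, non-hypertrophic ones, and Section 6.3 (item 4) excludes subjects with the other kind; the synopsis lists have neither condition. The same dosed subject can be eligible under one list and ineligible under the other. Other criteria, such as stable health, rest on the investigator's judgement. Second, the study is open-label without a DSMB or DMC, and Section 14 gives the investigator access to all study data. Eligibility could therefore be reassessed after events are known. This alleges no intent; it is the usual reason for keeping such judgements out of the definition of a safety set.

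Safety is the primary objective, the protocol says that there are no safety data in this population, and the sample is small: "Twenty subjects are planned; 10 kidney transplant recipients and 10 lung transplant recipients". A table with no serious events and a table with one would be read differently.

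**Working it through.** **Reproduction.** The plan gives no figure to reproduce. Section 15.6 calls the sample a descriptive pilot that is not powered, and no expected event rate or number of ineligible enrolments is stated.

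**The texts side by side.**

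1. *Randomized* (synopsis): in a single-arm study nobody is randomized. The word is best read as left-over wording that selects the same people as *enrolled*.
2. *Eligible*, entry reading: under Sections 4.1 and 8.1, those enrolled and supplied with drug are the eligible ones. The word then adds nothing and both texts select the same subjects.
3. *Eligible*, literal reading: Section 13 foresees subjects who fail the criteria. Such a subject, once dosed, is not eligible and so falls outside 15.1, but meets the synopsis definition.
4. No section says which reading applies, or that such a subject stays in.

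**Size, for illustration.** Inputs: n = 20, or 10 in one transplant group (Section 4.1). The number dropped (one) and the event counts are assumptions. With x subjects having the event, dropping one dosed subject shifts the rate as follows:

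- dropped subject had the event: (x − 1)/(n − 1) − x/n = −(n − x)/[n(n − 1)]
- dropped subject had no event: x/(n − 1) − x/n = x/[n(n − 1)]

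For n = 20, n(n − 1) = 380; for n = 10 it is 90. Intervals are exact (Clopper-Pearson) 95%: lower limit Beta(0.025; x, n − x + 1), upper limit Beta(0.975; x + 1, n − x). For x = 0 the lower limit is 0 and the upper limit is 1 − 0.025^(1/n), so for n = 19 it is 17.6%.

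| Assumed case | All dosed subjects kept | One dropped as ineligible | Shift, percentage points |
|---|---|---|---|
| Only serious event is in the dropped subject | 1/20 = 5.0% (0.1 to 24.9) | 0/19 = 0% (0 to 17.6) | −19/380 = −5.0 |
| Only serious event is in another subject | 1/20 = 5.0% (0.1 to 24.9) | 1/19 = 5.3% (0.1 to 26.0) | +1/380 = +0.3 |
| Common event, dropped subject had it | 10/20 = 50.0% | 9/19 = 47.4% | −10/380 = −2.6 |
| One group of 10, only event is in the dropped subject | 1/10 = 10.0% (0.3 to 44.5) | 0/9 = 0% (0 to 33.6) | −9/90 = −10.0 |
| No dosed subject judged ineligible | unchanged | unchanged | 0 |

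The shift is largest for a rare event that falls in the dropped subject, and shrinks as the event becomes more common. If all 20 had an adverse event, the any-event rate would not move: −(20 − 20)/380 = 0.

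**The case against.** The strongest reply is that *eligible* is entry wording. Section 8.1 uses nearly the same phrase for everyone who is given the drug, and 15.1 only adds receipt of a dose. Section 13 prescribes a signed form kept in the regulatory binder and names no effect on any analysis set. The protocol defines no per-protocol set, and Section 12.1 asks that subjects who stop treatment be encouraged to complete the remaining visits, which fits keeping them in. This stands to the extent that the plan does not order the exclusion of ineligible treated subjects. A reader might infer that it does, but the documents only leave the case open.

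Events would also not vanish from the record. Section 9.1.10 says "Information regarding occurrence of adverse events will be captured throughout the study", and Section 11.2.1 has all serious events documented and reported to the IRB. Only the tabulated rates are exposed, in a descriptive study with no test or threshold. That stands too. Section 15 promises a SAP before the final analysis that may modify these definitions. It is a natural place to settle the matter, but the present text does not settle it.

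Two further readings are tempting and not supported:

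- *That the word* randomized *shrinks or empties the synopsis set.* It is out of place, but no sensible reading removes anyone by it.
- *That the post-baseline condition also hides events of treated subjects.* The condition is the same in both texts. Section 5.3 counts adverse event reporting as a safety evaluation, so a reported post-dose event plausibly satisfies the condition by itself. What it leaves out is a subject with no post-dose information at all, and whether to count such a subject is a debatable trade-off.

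**Conclusion.** The point holds as a low-cost clarification. The two definitions of the primary safety set differ on eligibility, and a literal reading of 15.1 would let a dosed subject later judged ineligible, and that subject's events, leave the primary rate. The entry-only reading is plausible but is nowhere confirmed.

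The size is conditional. It is zero if no dosed subject is judged ineligible. If one is, and is dropped, a single serious event changes from 5.0% to 0% or to 5.3%, depending on whose event it is, and a common event moves by under 3 points. A reader might take the 0/19 case as the expected effect. It is not: it needs an eligibility breach, the trial's only serious event in that same subject, and an analyst who takes the literal reading. The documents give no rate for any of these. Confidence is moderate, because the outcome depends on which reading the SAP adopts.

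**What to change.** Use one exposure-based definition in the synopsis and in Section 15.1, and carry it into the SAP. Delete *eligible* and *randomized*. Suggested wording: *The safety population comprises every subject who receives at least one dose of study drug and has at least one post-baseline safety evaluation, regardless of any later finding that the subject did not meet the entry criteria. Such subjects are listed as protocol violations.*

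The post-baseline condition is carried over unchanged. With this wording the safety set no longer depends on which eligibility list is applied.

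The cost is one sentence in each place and possibly one extra line in a listing. No visit, procedure or treatment changes. It is best done before data accrue, since the study is open-label.

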15.2 Demographic and Baseline Characteristics

The following demographic variables at screening will be summarized: race, gender, age, height and weight.

15.3 Analysis of Primary Endpoint

This is a small descriptive study, with the primary safety endpoint of the incidence rate of patients who experience:

1) Any adverse event (AE) ascertained by patient report, physician evaluation, or laboratory value, 2) One or more serious adverse events (SAE) as defined by CTCAEv4, and 3) Adverse events leading to study drug discontinuation.

Adverse events will be explored for trends or heterogeneity between the two transplant subgroups; thoracic and abdominal. If there is evidence for a difference between groups, the subgroups will be reported separately.

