	
safety evaluation.
 
Adverse events will be explored for trends or heterogeneity between the two transplant subgroups; lung and kidney. If there is evidence for a difference between groups, the subgroups will be reported separately.
 
The mean maximum LSR composite score, the VAS score, and the Skindex-16 scores and trend in scores over the study visits will be reported as descriptive data. The composite LSR score will be compared to historical controls (Lebwohl et al, NEJM 2012).
 
The efficacy analysis will be based on the intent-to-treat (ITT) population. In the ITT population, patients will be counted in the treatment group upon informed consent, regardless of receiving any dose of study medication.
 
For efficacy analysis, all missing values due to patient early termination from the study will be imputed using last observation carried forward (LOCF) method, as appropriate. For each patient, the Baseline values will be defined as those values recorded at Day 1 prior to dosing or Screening as appropriate. Patients who are lost-to-follow-up after Baseline will be included to the ITT population carrying forward their Baseline values, i.e., these patients will be considered as treatment failures.
 
Percent reduction in number of actinic keratoses and proportions of patients with partial and complete clearance of actinic keratoses will be presented descriptively and visualized as histograms. These scores will be compared to historical controls (Lebwohl et al, NEJM 2012).

Rationale for Number of Subjects
	
This is a pilot descriptive sample, not powered for analysis. The sample size of 20 patients is selected to achieve a reportable sample size in two subgroups of organ transplant recipients.

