2.1 Risk / Benefit Assessment

The risks of ingenol mebutate are primarily local site reactions of redness, flaking, crusting, swelling, blisters, or erosions. These typically begin at day 1 of treatment. The adverse reactions reported in $\geq 2\%$ of patients treated with ingenol mebutate were application site pain, pruritus, and infection; periorbital edema, and headache. We will monitor the patients at day 4 and counsel them on mitigating site reactions with gentle skin care, cold packs, pain control if needed. Patients will also be counseled to carefully avoid the eye and lip area. We expect the infection rate in OTR to be less than the reported

rate of 3% as the majority of OTR are on routine antibiotic prophylaxis; any infections will be recorded as adverse events and treated according to standard of care.

If a patient has a (1) local skin response score of 3 or greater in any individual category, and (2) associated symptoms unrelieved by supportive care such as ice packs and nonsteroidal anti-inflammatory drug (NSAID), then 1% topical hydrocortisone cream or ointment is allowed after Day 4 at the discretion of the investigator.

Ingenol mebutate has accepted benefits for AK which outweigh the risks. OTR have a high burden of AK and frequently require multiple rounds of field treatment to reduce this sign of ultraviolet radiation induced skin damage. Other treatments require long-term applications or in-office light; ingenol has the benefit of being a short course. Ingenol mebutate is approved for immunocompetent patients, but there is no safety data in OTR. Despite this, the medication has been frequently used off-label in OTR and is generally believed to be safe due to the absence of systemic absorption. One recent case reported brisk local site reaction without systemic adverse events.

It is difficult to obtain insurance coverage for ingenol mebutate in OTR without demonstrating failure of multiple other treatments for AK. Participants in this study will also benefit from access to ingenol mebutate.

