15.6 Sample Size and Randomization

This is a pilot descriptive sample, not powered for analysis. The sample size of 20 patients is selected to achieve a reportable sample size in two subgroups of organ transplant recipients.

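### N = 20 is justified only by two reportable transplant subgroups, yet adverse events are promised by organ only if an undefined difference is observed

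*Combined protocol and SAP*

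**What the plan says.** The sample size has one rationale. The synopsis (Rationale for Number of Subjects) states: "The sample size of 20 patients is selected to achieve a reportable sample size in two subgroups of organ transplant recipients". Section 15.6 repeats it and adds that the sample is a descriptive pilot without power. Section 4.1 sets the split: "Twenty subjects are planned; 10 kidney transplant recipients and 10 lung transplant recipients". It gives the reason for choosing these organs: "These populations have been selected as they represent the spectrum of solid organ transplantation". It describes kidney recipients as having lower immunosuppression and skin cancer risk, and lung recipients as having the highest burden.

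The primary endpoint is the incidence of patients with any adverse event, with a serious adverse event, and with an adverse event leading to discontinuation of study drug. Section 15.3 and the synopsis say adverse events will be explored across the two subgroups and then set a condition: "If there is evidence for a difference between groups, the subgroups will be reported separately".

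Section 15 defers detail: "Prior to the analysis of the final study data, a detailed Statistical Analysis Plan (SAP) will be written".

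The subgroup labels differ. The synopsis speaks of "trends or heterogeneity between the two transplant subgroups; lung and kidney", while Section 15.3 calls the groups thoracic and abdominal.

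**The concern.** The design is built to describe two groups, but the analysis text promises the description only if the data show a difference. It does not say what counts as evidence, on which of the three components, or who decides. It does not say that counts by organ will be withheld otherwise, but no section commits to showing them.

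Two things follow. If the groups are split because the observed gap was large, the gap shown tends to exceed the true one. If they are pooled, the reader may have no counts by organ, and pooling is the usual outcome for rare components even when the true rates differ. The subgroup description that justifies N = 20 would then be either selected or missing.

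The overall incidence is reported either way. Lack of power is not the complaint, since the study is openly descriptive.

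**Working it through.** **Inputs from the documents**

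- N = 20, justified as "selected to achieve a reportable sample size in two subgroups of organ transplant recipients" (Section 15.6; same in the synopsis).
- 10 kidney and 10 lung recipients (Section 4.1). Check: 10 + 10 = 20, which agrees. No alpha, power, event rate or interval width is given, so nothing else about N can be reproduced.
- No rule for splitting the groups (Section 15.3, synopsis).
- The only numerical rate for a specific event is 3% for infection (Section 2.1). It is not a primary component, and the section expects a lower rate in transplant recipients. It serves only as a low-rate example.

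**Assumptions.** All true rates and splitting rules below are assumed, with no losses. Section 12.4 allows no replacement, so a group could end below 10.

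**Method.** Let X ~ Bin(10, p₁) and Y ~ Bin(10, p₂), independent. Then P(split) = Σ P(X = a)·P(Y = b) over all pairs (a, b) that meet the rule. The mean gap shown is the average of (b − a)/10 over those pairs, weighted by their probabilities.

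*Example, p₁ = p₂ = 0.03, gap of at least 3 patients.* P(0) = 0.7374, P(1) = 0.2281, P(≥3) = 0.00276, P(≥4) = 0.00015. The leading terms are 2 × 0.7374 × 0.00276 + 2 × 0.2281 × 0.00015 ≈ 0.0041.

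**Equal true rates: chance of a split**

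| True rate in both groups | Gap ≥ 3 patients | Gap ≥ 2 patients |
|---|---|---|
| 3% or 97% | 0.4% | 5% |
| 5% or 95% | 1.4% | 11% |
| 10% or 90% | 6.0% | 24% |
| 20% or 80% | 16% | 39% |
| 30% or 70% | 22% | 46% |
| 40% or 60% | 25% | 49% |
| 50% | 26% | 50% |

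If evidence means a two-sided Fisher p ≤ 0.05, the chance is at most 1.3% (at 50%). With no events in one group, the other needs 5: 0 v 4 gives p = 0.087 and 0 v 5 gives p = 0.033.

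**Unequal true rates, gap of at least 3 patients**

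| True rates | True gap | P(split) | Mean gap if split | Mean gap if pooled |
|---|---|---|---|---|
| 3% v 10% | 7 points | 5.6% | 31 points | 6 points |
| 5% v 20% | 15 points | 23.5% | 34 points | 9 points |
| 10% v 30% (or 70% v 90%) | 20 points | 39% | 37 points | 9 points |
| 30% v 50% | 20 points | 43% | 37 points | 7 points |

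Check on the last row: 0.432 × 37.2 + 0.568 × 6.9 = 16.1 + 3.9 = 20.0 points. The unconditional display is unbiased; the condition separates it into an inflated part and a deflated part.

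Under the Fisher rule, 10% v 30% is split 5.7% of the time and 30% v 50% is split 5.5%, the latter with a mean shown gap of 61 points.

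**Precision if both groups are always shown (Clopper-Pearson 95%)**

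- 0/10: upper limit 1 − 0.025^(1/10) = 30.8%.
- 0/20: upper limit 1 − 0.025^(1/20) = 16.8%.
- 9/10: 55.5% to 99.7%.

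**Labels.** Under Section 4.1, lung equals thoracic and kidney equals abdominal, so the patients are the same. The labels diverge only if another organ is enrolled, which the inclusion criteria in Section 6.2 allow.

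**The case against.** The strongest reply is that little is at stake. The study is small, descriptive and unpowered. No test or claim of difference is planned, and the overall result does not change. Reporting separately may mean separate rather than pooled headline results, with counts by organ still tabulated. The later SAP could define the trigger or drop it. The figures rest on assumed rules and rates, and with equal true rates they run from about 0% to 50%, so they fix no size for this trial. Exact intervals go beyond what is needed to cure the defect, and a change confined to adverse events leaves Section 15.4 without an organ breakdown for the secondary endpoints.

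Much of this stands. The overall result is safe, the numbers are illustrations, and counts may be shown anyway. The intervals are desirable rather than essential, and the Section 15.4 remark is fair. The defect remains: the text states a condition based on the results and makes no commitment outside it. A threshold defined in the SAP would still tie the display to the observed gap. If the SAP removed the condition, that would be the change asked for here. A descriptive aim also favours showing both groups, because description needs no evidence threshold.

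**Conclusion.** The concern holds. The rationale for N = 20 and the reporting rule for the primary endpoint do not fit together: the subgroups justify the sample size, but their adverse event results are promised only on an undefined condition that depends on the data.

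The consequence varies with how the condition is read. A Fisher test at 0.05 would rarely split the groups, so the breakdown would usually not be promised. A gap of 2 or 3 patients would split them by chance in up to 50% or 26% of trials and would show exaggerated gaps. These sizes rest on 10 evaluable patients per group and on assumed rules and rates. The conclusion itself rests only on the text. The change should be made, but the harm is confined to the subgroup description. The label mismatch is minor.

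**What to change.** Delete the conditional sentence in the synopsis and in Section 15.3, and replace it with:

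> Each of the three primary components will be reported as n/N (%) with exact 95% confidence intervals for kidney, lung and overall, whatever the observed difference. The difference between subgroups will be described without a hypothesis test.

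Use one subgroup label in the synopsis, Section 4.1 and Section 15.3, and state how a recipient of another organ would be classified if one is enrolled. Carry the same wording into the SAP.

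The cost is two table columns and a text edit, with no extra patients, visits or data. The downside is openly wide subgroup intervals, which show what 10 patients per group can support. Giving n/N by group also reveals any shortfall from withdrawals.
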